Grade 3 ALT (>5-20 x ULN) or Grade 3 bilirubin (>3-10 x ULN)	
 • Hold neratinib and capecitabine until recovery to Grade ≤1 for patients with ALT Grade ≤1 at baseline OR Grade ≤2 for patients with Grade 2 ALT at baseline. • Evaluate alternative causes. • For patients with ALT Grade ≤1 at baseline: resume at a reduced doses of neratinib 160 mg and capecitabine at 1100 mg/m² (550 mg/m² BID)^a if recovery to Grade ≤1 occurs within 3 weeks. If Grade 3 ALT or bilirubin occurs again despite the above-mentioned dose reduction, permanently discontinue neratinib and capecitabine. • For patients with Grade 2 ALT at baseline due to liver metastases: contact the Sponsor for guidance on appropriate dose adjustments.
Grade 4 ALT (>20 x ULN) or Grade 4 Bilirubin (>10 x ULN)	
 • Permanently discontinue neratinib and capecitabine. • Evaluate alternative causes.

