• 1st appearance	• Hold lapatinib and capecitabine until event resolves to Grade ≤ 1 ; then resume lapatinib dose at 1250 mg and capecitabine at the starting dose level.
• 2nd appearance	• Hold lapatinib and capecitabine until event resolves to Grade ≤ 1 ; then resume lapatinib dose at 1000 mg and capecitabine dose at 1500 mg/m ² (750 mg/m ² BID).
• 3rd appearance	• Discontinue lapatinib permanently. • Hold capecitabine until event resolves to Grade ≤ 1 ; then resume capecitabine at 1000 mg/m ² (500 mg/m ² BID).
• 4th appearance	• Discontinue capecitabine permanently.
Grade 3 adverse reaction	
• 1st appearance	• Hold lapatinib and capecitabine until event resolves to Grade ≤ 1 ; then resume lapatinib dose at 1250 mg and capecitabine dose at 1500 mg/m ² (750mg/m ² BID).
• 2nd appearance	• Hold lapatinib and capecitabine until event resolves to Grade ≤ 1 ; then resume lapatinib dose at 1000 mg and capecitabine at 1000 mg/m ² (500 mg/m ² BID).
• 3rd appearance	• Discontinue lapatinib and capecitabine permanently.
Grade 4 adverse reaction	
1st appearance	• Discontinue lapatinib and capecitabine permanently OR if Investigator deems it to be in the patient's best interest to continue, hold lapatinib and capecitabine until resolved to Grade ≤ 1 ; then resume lapatinib at 1000 mg and capecitabine at 1000 mg/m ² (500 mg/m ² BID).

Abbreviations: BID, twice daily; NCI CTCAE v.4.0: National Cancer Institute Common Terminology Criteria for Adverse Events Version 4.0.

Gastrointestinal Toxicity

Guidelines for dose adjustments of **lapatinib** and **capecitabine** for gastrointestinal toxicity are shown in Table A2. 9.

Table A2. 9 Gastrointestinal Toxicities Requiring Dose Adjustment of Lapatinib and Capecitabine

NCI CTCAE v.4.0	Action
Grade 1: Increase of <4 stools per day over baseline; mild increase in ostomy output compared to baseline.	
 Continue lapatinib and capecitabine at starting dose. Instruct patient to follow dietetic recommendations provided at the start of the study. Fluid intake of ~2L should be maintained to avoid dehydration.

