Abbreviations: ADL: activities of daily living; BID, twice daily; IV: intravenous; NCI CTCAE v.4.0: National Cancer Institute Common Terminology Criteria for Adverse Events Version 4.0.

Pulmonary Toxicity

Guidelines for adjusting doses of lapatinib in the event of pulmonary toxicity are shown in [Table A2. 10](#).

Table A2. 10 Pulmonary Toxicities Requiring Dose Adjustment of Lapatinib

NCI CTCAE v.4.0	Action
Grade \geq3 Pneumonitis/Interstitial Lung Disease: Severe symptoms; limiting self-care ADL; oxygen indicated.	Discontinue lapatinib treatment permanently.

Abbreviations: ADL: activities of daily living; NCI CTCAE v.4.0: National Cancer Institute Common Terminology Criteria for Adverse Events Version 4.0.

Hepatic Toxicity

Guidelines for adjusting doses of **lapatinib** and **capecitabine** in the event of hepatic toxicities are shown in Table A2. 11.

Table A2. 11 Liver Function Test Abnormality Requiring Dose Adjustment of Lapatinib and Capecitabine

NCI CTCAE v.4.0		Action
ALT or AST Grade 3: >5-20 x ULN; >5 x ULN for >2 weeks. OR ALT or AST Grade 4: >20 x ULN AND Total bilirubin > 2 x ULN		
 Discontinue lapatinib permanently.
Grade 3 hyperbilirubinemia (>3-10 x ULN)		
 Discontinue lapatinib permanently. Hold capecitabine until hyperbilirubinemia resolves or decreases to Grade 1 (ULN-1.5 x ULN) or Grade 2 (>1.5 x ULN). Reduce next capecitabine dose to 1500 mg/m² (750 mg/m² BID).
Grade 4 hyperbilirubinemia (>10 x ULN)		
 Discontinue lapatinib and capecitabine permanently. OR If the Investigator deems it to be in the patient's best interest to continue, hold capecitabine until event has resolved to Grade ≤ 1 (ULN-1.5 x ULN). If the Investigator decides to resume capecitabine, reduce capecitabine dose to 1000 mg/m² (500 mg/m² BID).
LAPATINIB Dose Adjustment in Subjects with Severe Hepatic Impairment (Child-Pugh Class C)		
Test	Result	
 HER2+ MBC: Reduce lapatinib dose to 750 mg. HR+, HER2+ breast cancer: Reduce lapatinib dose to 1000 mg.
Total bilirubin	≥2 mg/dL; ≥34 μmol/L	
Serum albumin	≤35 g/L	
PT INR	≥1.7	
Ascites	Mild to Severe	
Hepatic encephalopathy	Grade 1-2 (or suppressed with medication) Grade 3-4	

Abbreviations: ALT: alanine aminotransferase; AST: aspartate aminotransferase; NCI CTCAE v.4.0: National Cancer Institute Common Terminology Criteria for Adverse Events Version 4.0; ULN: upper limit of normal.

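### Table A2.11 leaves an isolated Grade 4 ALT/AST on lapatinib to the general rule, which permits rechallenge, and has no allowance for Grade 2 ALT at baseline

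*Protocol*

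**What the plan says.** Appendix 2 of the protocol gives each arm its own liver table.

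- **Arm B, Table A2.11.** One row holds the transaminase rule, with two limbs joined by OR: "ALT or AST Grade 3: >5-20 x ULN; >5 x ULN for >2 weeks", and "ALT or AST Grade 4: >20 x ULN AND Total bilirubin > 2 x ULN". The action is a permanent stop of lapatinib. The row gives no instruction for capecitabine and says nothing about baseline values.
- **Arm A, Table A2.4.** The Grade 4 trigger is "Grade 4 ALT (>20 x ULN) or Grade 4 Bilirubin (>10 x ULN"), with no bilirubin condition attached to the ALT. The action for that row, as for a Grade 3 recurrence after dose reduction, is to "permanently discontinue neratinib and capecitabine". The table also sets a recovery target of Grade ≤2 "for patients with Grade 2 ALT at baseline". Where that Grade 2 is due to liver metastases, it tells the site to "contact the Sponsor for guidance on appropriate dose adjustments".
- **Arm B, Table A2.8 (general toxicities).** At Grade 4 the first-listed action is a permanent stop of both drugs. The alternative, if the investigator judges it to be in the patient's "best interest to continue, hold lapatinib and capecitabine until resolved to Grade" ≤1, is "then resume lapatinib at 1000 mg and capecitabine at" 1000 mg/m² daily.
- **Section 6.1.3** holds lapatinib for toxicity of Grade 2 or worse until Grade ≤1. It treats the dose rules as a floor that sites must meet and may exceed.
- **Section 10.1** requires discontinuation once a product has been withheld for an AE for more than 28 days. In both arms it lets the Medical Monitor agree to something else.
- **Exclusion Criterion 8** admits ALT/AST up to 5 x ULN in patients with liver metastases, in both arms.

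**The concern.** A liver table exists so that sites do not have to improvise on a severe hepatic signal. In Arm B, one such signal, a transaminase above 20 x ULN without raised bilirubin, is not in the liver table at all. The rule that catches it allows lapatinib to be given again. The same ALT in Arm A ends treatment.

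The second gap concerns patients whom the protocol knowingly enrolls. Someone with liver metastases may enter with Grade 2 ALT. Arm A's table provides for her. Arm B's does not, so if lapatinib is held for an ALT rise, the general rules ask her to reach a grade better than the one she entered with.

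At stake are patient safety in the first case, avoidable loss of lapatinib in the second, and consistent handling across about 200 centers in both.

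**Working it through.** No sample size, power or alpha figure depends on this point. The check is to run cases through the text.

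**Step 1. Does any grouping of the row cover a single isolated Grade 4 value?** The row can be grouped in four ways, according to whether the two-week phrase is an alternative or a requirement, and whether the bilirubin condition applies to Grade 4 only or to both limbs. The test case is a single ALT of 25 x ULN with bilirubin 1 x ULN.

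| Grouping that stops lapatinib | Test case |
|---|---|
| Grade 3 of any duration, OR (Grade 4 AND bilirubin >2 x ULN) | Not covered |
| Grade 3 lasting >2 weeks, OR (Grade 4 AND bilirubin >2 x ULN) | Not covered |
| (Grade 3 OR Grade 4) AND bilirubin >2 x ULN | Not covered |
| (Grade 3 lasting >2 weeks OR Grade 4) AND bilirubin >2 x ULN | Not covered |

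The reason is the same each time: 25 is above the Grade 3 ceiling of 20, and bilirubin of 1 does not exceed 2. As a control, ALT 25 x ULN with bilirubin 2.5 x ULN is covered by all four. The finding is limited to a single value. An ALT above 20 x ULN that lasts more than two weeks might be caught by the two-week phrase if that phrase is not capped at 20 x ULN.

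**Step 2. Where does the value go?** Section 6.1.3 refers to Appendix 2 for the detailed rules, so I take Table A2.8 as governing. The investigator may stop both drugs, or hold to Grade ≤1 and resume:

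- lapatinib at 1000/1250 = 80% of the starting dose;
- capecitabine at 1000/2000 = 50% of the starting dose.

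**Step 3. Compare with the neighboring rules.** In Arm A, ALT 25 x ULN is a permanent stop of both drugs. Table A2.4 names ALT only, so the comparison is exact for ALT and not for AST. Within Arm B, lapatinib is stopped permanently for Grade 3 hyperbilirubinemia (Table A2.11) and for Grade 4 diarrhea (Table A2.9). An isolated Grade 4 transaminase is therefore treated more leniently than other severe events in the same arm.

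**Step 4. The baseline gap.** The enrollment ceiling with liver metastases is 5 x ULN, and Grade 3 begins above 5 x ULN. The rise needed to reach that threshold, for assumed entry values, is:

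- entry 4.0 x ULN: 5/4.0 − 1 = 25%
- entry 4.5 x ULN: 5/4.5 − 1 = 11%
- entry 5.0 x ULN: 5/5.0 − 1 = 0%

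A modest rise is enough. If lapatinib is then held under Table A2.8 or Section 6.1.3, the target is Grade ≤1, and the 28-day limit in Section 10.1 runs. The same patient in Arm A has a written target of Grade ≤2. Elsewhere the protocol accepts baseline as an endpoint: Section 8.2.1 for repeat laboratory tests, and Table A2.9 for diarrhea in Arm B.

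**The case against.** The strongest reply is that nothing is unhandled. Table A2.8 covers an isolated Grade 4 value, lists a permanent stop of both drugs first, and allows resumption only on a best-interest judgment, after recovery and at reduced doses. Stop-or-discretion is also the protocol's usual Grade 4 pattern: general toxicity in Arm A, hematologic toxicity in both arms, and capecitabine for Grade 4 bilirubin in Arm B. Two drugs may properly have different rules, and the lapatinib thresholds may follow the labeling that Section 6.1.2 cites, which is not available here.

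Most of this stands. Arm B does have a rule, and a difference between arms is not an error in itself. It does not explain why a Grade 4 transaminase permits rechallenge in the arm that ends lapatinib for Grade 3 hyperbilirubinemia.

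On the baseline gap, the reply is that the Medical Monitor clause in Section 10.1 gives a way out, that Arm A's rule for these patients also ends in Sponsor contact, and that an elevation present at entry is arguably not a toxicity. The first two soften the consequence. The third helps with a value that merely stays at Grade 2, but once ALT rises above 5 x ULN and lapatinib is held, the only written target in Arm B is Grade ≤1.

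**Conclusion.** Both gaps are real and worth closing. The isolated Grade 4 omission holds on every grouping of the row. The missing baseline allowance is a plain absence from Table A2.11. The documents give no count of affected patients; it is probably small. No effect on PFS or OS is claimed.

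Three stronger readings are tempting, and the documents do not support them:

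- A reader might infer that Arm B's rule runs backwards by severity, because an isolated Grade 3 value stops lapatinib for good while an isolated Grade 4 value does not. This follows on only one of the four groupings. The table cell was flattened in the PDF text, and its layout may settle which grouping is meant. The Grade 3 rule is not challenged here.
- A reader might infer that Arm B has no stop for an isolated Grade 4 value. Table A2.8 lists one first.
- A reader might infer that a patient with baseline Grade 2 ALT must lose lapatinib. Section 10.1 lets the Medical Monitor agree otherwise.

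The baseline conclusion assumes that lapatinib is held. If the row is meant to stop lapatinib at any Grade 3 value, no recovery target arises for that value.

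**What to change.** Make two additions to Table A2.11.

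(a) Grade 4 ALT or AST above 20 x ULN, at any bilirubin: discontinue lapatinib permanently. State that capecitabine stays under Table A2.8, since the present row does not mention it.

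(b) Grade 2 ALT at baseline due to liver metastases: where lapatinib is held and no permanent-stop criterion is met, the recovery target is Grade ≤2, with Sponsor contact on the dose, as in Table A2.4. This changes the target only and overrides no stop rule.

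Leave the Grade 3 rule alone. Rewriting it so that an isolated Grade 3 value goes to Table A2.8 could loosen a liver stop rule, because a first Grade 3 event there resumes lapatinib at the full 1250 mg.

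The sponsor's clinical team should confirm both additions against the lapatinib labeling.

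The cost is one table amendment and a memo to sites. Investigators in Arm B lose some discretion at Grade 4, and for an isolated AST the rule becomes stricter than Arm A's liver table, which names ALT only. No tests are added: ALT, AST and bilirubin are already measured on Day 1 of each cycle and repeated when abnormal.

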4 OVERALL DESIGN AND PLAN OF THE STUDY

4.1 Study Design

This is a randomized, multi-center, multinational, open-label, active-controlled, parallel design study of the combination of neratinib plus capecitabine versus the combination of lapatinib plus capecitabine in HER2+ MBC patients, who have received two or more prior HER2-directed regimens in the metastatic setting.

Patients will be randomized in a 1:1 ratio to one of two treatment arms:

- Arm A: neratinib (240 mg once daily) + capecitabine (1500 mg/m² orally daily, 750 mg/m² twice daily [BID])
- Arm B: lapatinib (1250 mg once daily) + capecitabine (2000 mg/m² orally daily, 1000 mg/m² BID)

Following a 21-day screening period (Section 9.1), eligible patients will be randomized to Arm A or Arm B. Baseline assessments will be performed prior to randomization. Following randomization, patients will participate in the active treatment phase, consisting of 21-day treatment cycles (Section 9.2). Investigational products will be administered orally by patients as described in Section 6.1. Neratinib and lapatinib are to be taken continuously, in 21-day cycles, with no rest between cycles. Capecitabine will be taken on Days 1 to 14 of each 21-day cycle.

Clinic visits during the active treatment phase are planned on Days 1, 8, and 15 of Cycle 1 and on Day 1 of each subsequent cycle. Assessments required throughout the study are summarized in the Schedule of Procedures (Appendix 1) and a diagram of the study schema is provided in Figure 1.

Patients may be discontinued from investigational product(s) or from the study, as described in Sections 10.1, 10.2 and 11.

The co-primary endpoints are independently adjudicated PFS and OS. The secondary endpoints are investigator-assessed PFS, ORR, DOR, CBR (CR, PR or SD \geq 24 weeks), health outcomes assessments, time to intervention for symptomatic metastatic CNS disease, AEs and SAEs (graded according to the National Cancer Institute [NCI] Common Terminology Criteria for Adverse Events Version 4.0 [CTCAE v.4.0]). An interim analysis of OS will be performed at the time of final PFS analysis (Section 12.6).

Approximately 600 patients will be enrolled at approximately 200 centers in North America, Europe including Israel, and the Rest of World (RoW). See Section 12.7 for a discussion of sample size.

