4.2 Randomization and Blinding

4.2.1 Randomization Scheme

Randomization will be managed and maintained centrally through an automated Interactive Voice Response System/Interactive Web Response System. Patients will be randomized in a 1:1 ratio to one of the two treatment arms.

Randomization will be stratified according to:

- The number of previous HER2-directed regimens in the metastatic setting ($N = 2$ or $N \geq 3$).
- Geographic region (North America vs. Europe, including Israel vs. RoW)
- Visceral vs. non-visceral only disease
- Estrogen receptor+ (ER+) and/or progesterone receptor (PR+) (i.e., hormone receptor +) versus ER- and PR- (i.e., hormone receptor -).

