5 STUDY POPULATION

5.1 Inclusion Criteria

Each patient will be entered into this study only if she/he meets all of the following criteria:

1. Aged ≥ 18 years at signing of informed consent.
2. Histologically confirmed MBC, current stage IV.
3. Documented HER2 overexpression or gene-amplified tumor (immunohistochemistry [IHC] 3+; or IHC 2+ with confirmatory fluorescence in situ hybridization [FISH]+). (Note: Patients who are IHC 0 or 1+ are not eligible to participate in the study). Tumor samples will be evaluated for HER2 expression by IHC (HercepTest™) and if required for gene amplification by FISH analysis (IQFISH pharmDx™).
4. Prior treatment with at least two HER2-directed regimens for metastatic breast cancer. A new regimen is defined as a modification in a planned course of therapy to include other treatment agents (alone or in combination) as a result of disease progression, relapse, or toxicity ([Rajkumar et al., 2011](#)). A new regimen also starts when a planned period of observation off therapy is interrupted by a need for additional treatment for the disease.
5. At least one measurable lesion as defined by Response Evaluation Criteria in Solid Tumors (RECIST v1.1 ([Eisenhauer et al., 2009](#)), see [Appendix 7](#)). Specifically, no ascites, pleural or pericardial effusions, osteoblastic bone metastases, or carcinomatous lymphangitis of the lung as the only lesion are allowed.
6. Left ventricular ejection fraction (LVEF) $\geq 50\%$ measured by multiple-gated acquisition scan (MUGA) or echocardiogram (ECHO).
7. Eastern Cooperative Oncology Group (ECOG) status of 0 to 1 (see [Appendix 3](#)).
8. Negative β -human chorionic gonadotropin (hCG) pregnancy test for premenopausal women of reproductive capacity (those who are biologically capable of having children) and for women less than 12 months after menopause.
9. Women of childbearing potential must agree and commit to the use of a highly effective method of contraception, as determined to be acceptable by the Investigator, from the time of informed consent until 28 days after the last dose of the investigational products. Men must agree and commit to use a barrier method of contraception while on treatment and for 3 months after last dose of investigational products.

10. Provide written, informed consent to participate in the study and follow the study procedures.

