6.1.3 Dose Adjustment

Investigational product dose adjustment and/or discontinuation should be performed according to [Appendix 2](#) and Section [10.1](#).

Recommended dose reductions for the -1 and -2 dose levels of neratinib are listed in [Table 2](#).

Table 2. Dose Reduction Levels for Neratinib-Related Toxicity

Dose Level	Neratinib
Starting Dose	240 mg
-1	160 mg
-2	120 mg

Recommended dose reductions for the -1 and -2 dose levels of capecitabine in combination with neratinib are listed in [Table 3](#).

Table 3. Dose Reduction Levels for Capecitabine-Related Toxicity (When Administered in Combination with Neratinib)

Dose Level	Capecitabine (administered in combination with neratinib)
Starting Dose	1500 mg/m ² , 750 mg/m ² BID
-1 ^a	1100 mg/m ² , 550 mg/m ² BID
-2 ^a	750 mg/m ² , 375 mg/m ² BID

Abbreviation: BID: twice daily

^aSince capecitabine is provided as 150 mg or 500 mg tablets, it is recommended that the capecitabine dose reduction(s) (to 75% [level -1] or 50% [level -2] of the starting dose) is rounded down to the nearest 500 mg or multiple of 150 mg for the BID dose. If the patient's body surface area is >2.0, the standard of care for the study center can be utilized for capecitabine mg/m² dosing.

The recommended dose reduction for the -1 dose level of lapatinib is listed in [Table 4](#). Lapatinib doses should be held in patients with an LVEF that is Grade ≥ 2 and in patients with an LVEF that decreases below the institution's lower limit of normal (LLN; <50% if not specified). Lapatinib (in combination with capecitabine) may be restarted at a reduced dose of 1000 mg/day after a minimum of 2 weeks, if the LVEF recovers to normal and the patient is asymptomatic.

Lapatinib doses should be held in patients with Grade ≥ 2 NCI CTCAE toxicity, until the toxicity improves to Grade ≤ 1 ; lapatinib may be restarted at 1250 mg/day. If the toxicity recurs, then lapatinib (in combination with capecitabine) should be restarted at a reduced dose of 1000 mg/day.

Table 4. Dose Reduction Levels for Lapatinib-Related Toxicity

Dose Level	Lapatinib
Starting Dose	1250 mg
-1	1000 mg (750 mg for severe hepatic impairment; see Appendix 2)

Recommended dose reductions for the -1 and -2 dose levels of capecitabine in combination with lapatinib are listed in [Table 5](#).

Table 5. Dose Reduction Levels for Capecitabine-Related Toxicity (When Administered in Combination with Lapatinib)

Dose Level	Capecitabine (administered in combination with lapatinib)

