7.3 Prohibited Concomitant Treatment

The following treatments are prohibited throughout the duration of the active (treatment) phase of the study:

- Any concurrent chemotherapy, radiotherapy (including palliative radiotherapy), surgery related to cancer, anticancer immunotherapy, or other anticancer treatments including other investigational agents, megestrol and hormonal agents.

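### Table A2.11 gives a hormone-receptor-positive Arm B patient with Child-Pugh C impairment two lapatinib doses, 750 mg and 1000 mg, and the 1000 mg line conflicts with Table 4

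*Protocol*

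**What the plan says.** The last block of Table A2.11 (Protocol Appendix 2, liver function abnormalities on lapatinib plus capecitabine) covers lapatinib dosing in Child-Pugh Class C impairment. Its action cell has two bullets. One reads "HER2+ MBC: Reduce lapatinib dose to 750 mg"; the other reads "HR+, HER2+ breast cancer: Reduce lapatinib dose to 1000 mg". The table does not say which governs when both apply.

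Table 4 in section 6.1.3 sets the lapatinib reduction levels. The start is 1250 mg and the -1 level is 1000 mg, with one exception in brackets: "750 mg for severe hepatic impairment; see Appendix 2". That exception does not depend on hormone receptor status.

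Four other parts of the protocol bear on how the bullets are read:

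- Section 5.1 requires "Histologically confirmed MBC, current stage IV" and "Documented HER2 overexpression or gene-amplified tumor".
- Section 4.2.1 makes hormone receptor status a randomisation stratum, so HR+ patients are expected in both arms.
- Section 4.1 gives one lapatinib regimen, "Arm B: lapatinib (1250 mg once daily) + capecitabine".
- Section 7.3 prohibits, during active treatment, "other anticancer treatments including other investigational agents, megestrol and hormonal agents".

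**The concern.** The two bullets look like mutually exclusive categories, but in this trial the first contains the second. A site with an HR+ Arm B patient in Class C can find printed support for either dose. Two sites could therefore treat the same kind of patient differently, each following the protocol.

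What is at stake is dosing safety in a small group with severe hepatic impairment, where too high a dose is the worry. The higher dose is also the one that disagrees with Table 4. Nothing here touches alpha, power or the PFS and OS analyses.

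**Working it through.** No published figure has to be reproduced. The check is one of set membership, followed by simple dose arithmetic.

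**Who meets each line**

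| Arm B patient in Child-Pugh C | HER2+ MBC line (750 mg) | HR+, HER2+ line (1000 mg) | Table 4 |
|---|---|---|---|
| HR- | applies | does not apply | 750 mg |
| HR+ | applies | applies | 750 mg |

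The first line applies to everyone because section 5.1 admits only HER2-positive stage IV disease. The HR+ patient is the only one given two doses.

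**Can the HR+ line be read as a specific exception?** On that reading 750 mg would be for HR- patients only. Table A2.11 does not say so, and Table 4 still gives 750 mg to all. The cross-references do not settle the order: Table 4 points to Appendix 2, and Appendix 2, section 1, points back to section 6.1.3 for the dose levels.

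**Could the HR+ line belong to another regimen?** Arm B has a single lapatinib regimen, with capecitabine, and hormonal agents are prohibited on treatment. The documents contain no HR+ regimen to which 1000 mg could refer.

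**Size of the dose gap**

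- Difference: 1000 - 750 = 250 mg/day; ratio 1000/750 = 1.33.
- Per 21-day cycle: 21 x 1000 - 21 x 750 = 21,000 - 15,750 = 5,250 mg.
- From the 1250 mg start: a cut of 500/1250 = 40% under one line and 250/1250 = 20% under the other.
- From the -1 level of 1000 mg (Table 4; also the reduced dose in Table A2.8): a cut of 250/1000 = 25%, or none.

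**How far other rules already cover these patients**

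The Child-Pugh block lists bilirubin from 2 mg/dL. The upper limit of normal (ULN) is not given; assume 1.0 to 1.3 mg/dL. Then 2.0/1.3 = 1.54 and 2.0/1.0 = 2.0 x ULN. Both exceed the 1.5 x ULN at which Table A2.11 starts Grade 2, so the lapatinib hold for Grade 2 or higher toxicity in section 6.1.3 would apply where the rise is classed as toxicity. Both are below the 3 x ULN above which Table A2.11 stops lapatinib permanently. The block also lists albumin, INR, ascites and encephalopathy, which the bilirubin stop does not address.

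**Possible number of patients (assumed proportions)**

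- Arm B: 600/2 = 300.
- HR+ share, assumed 40% to 60%: 120 to 180.
- Share of those reaching Class C while still on lapatinib, assumed 0% to 2%: 0 to 180 x 0.02 = 3.6.
- As a share of the trial: 0 to 3.6/600 = 0.6%.

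Neither proportion is in the documents.

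**The case against.** The strongest reply is that the protocol already points to 750 mg. Section 6.1.3 calls the adjustment rules the least an investigator must do. A patient who meets both lines satisfies the HER2+ MBC line and Table 4 only at 750 mg, and that dose also goes at least as far as the HR+ line asks. This is a fair argument for preferring 750 mg. It does not settle the matter, because no text ranks the two lines and an investigator giving 1000 mg is following a printed instruction written for that patient's receptor status.

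The second reply is that almost nobody will be dosed in this state, and most of it stands:

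- Entry requires ECOG 0 or 1 and excludes bilirubin above 1.5 x ULN and active hepatitis B or C.
- Grade 2 or higher toxicity holds lapatinib.
- Section 10.1 ends treatment on progression, or after a hold of more than 28 days for an adverse event, unless otherwise agreed with the Medical Monitor.
- Table A2.11 stops lapatinib for the listed ALT/AST and bilirubin elevations.

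These rules push the count toward zero but do not make the two lines agree. The toxicity holds may also not be triggered when hepatic decline is attributed to liver metastases, although progression would then often end treatment.

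Third, the documents do not show that 1000 mg is unsafe in Class C, and section 6.1.2 refers sites to the product labels. That is correct, and it is why the choice of dose needs the sponsor's clinical confirmation. A pointer to an outside source does not repair two conflicting lines in the protocol's own table.

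**Conclusion.** The concern holds. As written, Table A2.11 assigns both 750 mg and 1000 mg to an HR+ Arm B patient with Child-Pugh C impairment, and 1000 mg contradicts Table 4 on any reading. This follows from the text alone and needs no assumption.

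The practical reach is small: a 250 mg/day difference in 0 to about 4 patients. That range rests on the assumed HR+ and Class C proportions and should fall near its low end once the hold and stop rules are counted. The statistical design and analyses are unaffected. It is still an error in a safety dosing table and should be corrected.

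**What to change.** Delete the HR+ line from the Child-Pugh C cell of Table A2.11, subject to clinical confirmation by the sponsor. One dose then remains for every Arm B patient in this class: 750 mg, which is 750/1250 = 60% of the start and agrees with Table 4. If the sponsor does intend 1000 mg for HR+ patients, restrict the 750 mg line to HR- patients and split the Table 4 entry in the same way. Leave the Grade 2 or higher hold in section 6.1.3 as it is.

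The edit is one bullet. Section 14.3.1 requires a protocol amendment with IRB/IEC approval for any change to the study plan, so the real cost is that process plus a notice to about 200 centres. The cost is small if the edit travels with another amendment.
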